5.5 Subject Compliance Monitoring

Subjects will receive their first dose of study medication on study Day 1 in the doctor's office and after completion of the study assessments will have the topical eye drops dispensed for self-administration.

Subjects will be provided with diaries to record the time of each dose and will also be asked to record any adverse symptoms. In addition, they will be asked to make a note of any missed doses together with the reason for the omission. Subjects will be asked to bring their diaries with them at the 4, and 8 week visits. Diaries will be reviewed with the subject by a member of the research team at each visit. Additionally, subjects will be asked to bring back the used and unused drug eye droppers at each study visit. Participants will be asked to return the unused eye droppers each study visit as a method to determine compliance.

5.6 Prior and Concomitant Therapy

Prior medications are defined as all medications taken within 30 days prior to Day 1, whether there is continued use or not. Concomitant medications must be identified in the subject's medical record, including all lubricants administered for Dry Eye Disease. These medications will be recorded in the case report form (CRF).

- For each medication taken, the following information will be collected:
 - Medication trade name
 - Eye that was treated, if applicable
 - Indication for which the medication was given

- Date started
- Date stopped
- Dose of medication used.

In general, patients will be required to maintain the treatments that they were using at entry into the study throughout the follow-up period. Patients will be instructed to continue using the same brand of eye drops during the study as they were using at the screening visit. If patients are wearing contact lenses (Soft bandage contact lenses or PROSE lens) or using serum tears, they will be asked to discontinue contact lens wear or use of serum tears for 2-weeks prior to being enrolled (Baseline visit) and will be required to not wear contact lenses or use serum tears for the duration of the study (until week 10 visit). This is necessary as one of the proposed exploratory study outcome measure is corneal Staining. Contact lenses can directly reduce corneal epitheliopathy and staining due to ensconcing and acting like a bandage that prevents corneal exposure to tear fluid inflammatory materials. Thus, because of overlapping effects on the exploratory outcome measure, it may not be possible to attribute any observed clinical benefit to IVIG-eye drops treatment if contact lenses are used concurrently. This approach has been used in other clinical trials that have investigated the use of an anti-inflammatory agent in dry eye disease (NIH funded 'Dry Eye Evaluation and Management (DREAM) study').⁶⁴ Stopping contact lens wear may increase the risk of worsening of Dry Eye Disease (DED) during the wash-out period and during the course of the study. However, because other eye drop treatments will continue during the wash out period as well as during the course of the study, we do not expect any significant clinical worsening during the study. We do however expect the frequency of use of artificial tears to go up during the wash out period and during the course of the study.

Patients will be enrolled if they have been using their eye treatments for at least 30 day prior to the baseline visit and patients will be asked to commit to continue using the same treatments for the duration of the study. Participants will also be permitted to continue ancillary treatments such as eyelid massage or warm compresses of the eyelids. The number of drops and frequency must be recorded in the subject diary provided. The use of any investigational agent during past 30 days is prohibited.

The subjects will be monitored at 4 week intervals to ensure that they are not subjected to any undue risks during the course of the study. Additionally, they will be warned of the possible signs and symptoms of clinical worsening of DED, and advised to contact the research team immediately in case any of those symptoms occur. Subjects will also be encouraged to contact the research team in case they experience any ocular discomfort during the wash out period or during the course of the study. The subject's condition will be monitored by the physician (Principal Investigator) at each study visit, as well as at any interim visit (in case of adverse symptoms, as mentioned above). Any worsening of DED or any adverse event due to the study drug will be recorded. In case of clinical worsening, based on the individual subject's clinical condition, one or more of the following therapeutic decisions may be implemented: (1) Increasing/adding the use of artificial tears or ointments (2) Increasing/adding the use of anti-inflammatory therapy (Restasis/ Xiidra/ Steroids) or Serum Tears, (3) Withdrawal of the use of study drug (if worsening occurs during the course of the study). The decision will be made by the physician (Principal Investigator) based upon his clinical judgment as per the individual subject's clinical condition. If contact lens wear is instituted during the course of the study and/or the study drug is withdrawn, the subject will be withdrawn from the study. After any clinical worsening is noted, the subjects will be followed more closely (weekly) until complete resolution of symptoms and return to the subject's previous baseline. Subjects will be withdrawn from the study for presumed ocular allergic reaction to the product and ocular infection. The study will be stopped if the incidences of presumed ocular allergic reaction to the product and ocular infection surpasses 20% for each.

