4.4 Early Withdrawal of Subjects

4.4.1 When and How to Withdraw Subjects

Subjects have the right to withdraw from the study at any time, for any reason, without jeopardizing their medical care. Where possible, subjects will be followed for safety and encouraged to return for follow-up visits for any unresolved safety events.

The IRB and Investigator also have the right to withdraw subjects from the study for the following reasons: when continuation may jeopardize the health of the subject, protocol violations, adverse events or concurrent conditions, administrative or other reasons.

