All AEs and SAEs whether volunteered by the subject, discovered by study personnel during questioning, or detected through physical examination, laboratory test, or other means will be reported appropriately. For each adverse event, the following information will be recorded on the subject's Case Report Form(s): onset date, end date or continues, intensity, duration, relationship to test patch, action taken, and outcome. If a subject experiences a serious adverse event (SAE), study staff may discontinue the subject from study participation. The study staff must notify the IRB within 24 hours of receipt of the information. The study staff will instruct the subject to notify the research facility should any adverse event occur within 7 days of study completion. (For definitions of an AE and SAE, see below). Subjects who withdraw due to an adverse event may be replaced.

- **Serious Adverse Event:** An AE should be classified as an SAE if the following criteria are met:
 1. It results in death (i.e., the AE actually causes or leads to death.).
 2. It is life-threatening (i.e., the AE, in the view of the investigator, places the subject at immediate risk of death. It does not include an AE that, had it occurred in a more severe form, might have caused death.).
 3. It requires or prolongs inpatient hospitalization.
 4. It results in persistent or significant disability/incapacity (i.e., the AE results in substantial disruption of the subject's ability to conduct normal life functions).

5. It results in a congenital anomaly/ birth defect in a neonate/infant born to a mother exposed to the investigational medicinal product (IMP).
6. It is considered a significant medical event by the investigator based on medical judgement (e.g., my jeopardize the subject or may requires medical or surgical intervention to prevent any of the occurrences listed above.

To ensure consistency of AE and SAE causality assessments, the following general guideline will be applied:

Yes

There is a plausible temporal relationship between the onset of the AE and administration of the IVIG, and the AE cannot be readily explained by the subject's clinical state, intercurrent illness, or concomitant therapies; and/or the AE follows a known pattern of response to the IVIG; and/or the AE abates or resolves upon discontinuation of the IVIG or dose reduction and, if applicable, reappears upon re-challenge

No

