8.6 Serious Adverse Event Reporting

All Serious Adverse Events (SAE) that occur during the course of the study, including death, which are unanticipated require reporting to the IRB within **5 business** days of the investigator becoming aware. Serious adverse events will be recorded starting after first dose of study drug and continuing until the end of the study. The minimum information to be provided includes:

1. Protocol Number
2. Initial reporter
3. Subject identification
4. Nature and date of the event/effect
5. Country of the event/effect
6. Severity of the event/effect
7. Reporting criteria
8. Narrative description of the event/effect
9. Outcome if known
10. Causal relationship to the investigational product
11. Additional and follow-up information as requested by the medical monitor.

Events requiring reporting to the IRB within **15 business days** of the investigator becoming aware include:

1. Local adverse events or problems that are unanticipated and, while not meeting the criteria of serious, indicate research is associated with a greater risk of harm to participants or others than previously known.
2. New information indicating an unexpected change to the risks or benefits of the research (i.e., an unanticipated problem).
3. Administrative hold by investigator, regulatory authorities or other entities.

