8.8 Data Safety Management Plan

The study protocol will be reviewed and approved by the UIC IRB. Adverse events and compliance will be monitored. Research staff will be trained on the protocol requirements and data collection methods before completing study related procedures. Privacy, coding, storage: Research staff will be trained on the protocol requirements and data collection methods before completing study related procedures. Random study ID numbers will be assigned to study subjects. A master code list will link the subject MRN to the study ID number. The data collected will be stored on PI's desktop in a HIPPA compliant encrypted folder at the Ear and Eye Infirmary and Lions Eye Research building. The data collected, master code list will be accessible only to the PI and the research team involved in this project. The desktops will be password protected as well.

All Serious Adverse Events (SAE) that occur during the course of the study, and possibly related to the study intervention, including death, which are unanticipated will be reported to the IRB within 5 business days of the investigator becoming aware. A copy of the report will be sent to the FDA.

Events requiring reporting to the IRB within 15 business days of the investigator becoming aware include:

- Local adverse events or problems that are unanticipated and, while not meeting the criteria of serious, indicate research is associated with a greater risk of harm to participants or others than previously known.
- New information indicating an unexpected change to the risks or benefits of the research (i.e., an unanticipated problem).

A copy of this report will be sent to the FDA.

The minimum information to be provided includes:

1. Protocol Number
2. Initial reporter
3. Subject identification
4. Nature and date of the event/effect
5. Country of the event/effect
6. Severity of the event/effect

7. Reporting criteria
8. Narrative description of the event/effect
9. Outcome if known
10. Causal relationship to the investigational product
11. Additional and follow-up information as requested by the medical monitor.

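### No single treatment-related serious adverse event, of any kind, triggers a prespecified pause of the study; the only stopping rule waits for a 20% incidence of ocular allergy or infection

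*Combined protocol and SAP*

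**What the plan says.** Section 5.6 gives one rule that acts on the whole study: "The study will be stopped if the incidences of presumed ocular allergic reaction to the product and ocular infection surpasses 20% for each". It does not name the denominator, the arm or the times of checking.

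Every other safety provision acts on one subject or concerns reporting:

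- Section 8.1, on an SAE: "If a subject experiences a serious adverse event (SAE), study staff may discontinue the subject from study participation". It continues: "The study staff must notify the IRB within 24 hours of receipt of the information". It also allows subjects who withdraw because of an adverse event to be replaced.
- Sections 8.6 and 8.8 set reporting times. Under 8.8, SAEs that occur "and possibly related to the study intervention, including death, which are unanticipated will be reported to the IRB within 5 business days", with a copy to the FDA.
- Section 8.6 mentions a hold only in its list of matters to report within 15 business days: "Administrative hold by investigator, regulatory authorities or other entities". It gives no criterion for imposing one.
- Section 4.4.1: "The IRB and Investigator also have the right to withdraw subjects from the study for the following reasons". This power concerns subjects, not the study.
- Sections 5.6 and 5.7 provide rescue therapy, withdrawal of study drug and an optional code-break. After clinical worsening, Section 5.6 adds that "the subjects will be followed more closely (weekly) until complete resolution of symptoms".

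Section 8.9 gives primary oversight to the principal investigator. No monitoring committee is described.

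**The concern.** Section 1.7 states that IVIG has not been used as eye drops before, and Section 2 makes safe tolerance the main objective. The plan accepts that some harms should stop the study by rule, yet the rule it sets is a proportion. One related SAE leaves enrolment and first dosing of everyone else unchanged unless somebody chooses to hold the study. The provision for replacing withdrawn subjects means that recruitment may even be extended after such an event. What is at stake is whether new subjects are exposed before anyone independent of the investigator has reviewed the event.

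**Working it through.** **1. Sample size.** Section 7.1 wants 12 evaluable subjects per arm and allows for 10% attrition: 12/0.9 = 13.3, rounded up to 14 per arm, or 28 in all. This reproduces the plan's target and agrees with the 14 per group in Section 3.1.

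**2. What the 20% rule needs.** The smallest counts above 20% are:

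| Denominator | Count needed | One fewer |
|---|---|---|
| 14 (one arm) | 3 (21.4%) | 2 (14.3%) |
| 28 (all) | 6 (21.4%) | 5 (17.9%) |

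On either denominator one event falls well short. The gap therefore covers allergic and infectious SAEs as well as all others.

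**3. Chance of a related SAE on IVIG.** The documents give no SAE rate for topical IVIG, so the per-subject rate p is assumed. P(at least one in 14) = 1 − (1 − p)^14.

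- p = 1%: 1 − 0.869 = 13%
- p = 2%: 1 − 0.754 = 25%
- p = 5%: 1 − 0.488 = 51%

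**4. Total chance of a pause.** The research staff are masked, so a related SAE in either arm must count. P(pause) = 1 − (1 − p_IVIG)^14 × (1 − p_saline)^14.

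- 1% and 1%: 1 − 0.869 × 0.869 = 24.5%
- 2% and 1%: 1 − 0.754 × 0.869 = 34.5%
- 5% and 1%: 1 − 0.488 × 0.869 = 57.6%

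In the second case, the chance that saline events alone cause the pause is (1 − 0.869) × 0.754 = 9.9%.

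**5. Who is affected when it happens.** Assume one enrolment per week, 28 subjects, and one SAE at a random time in the index subject's 8 dosing weeks. Let j be the number enrolled after the index subject (0 to 27, mean 13.5) and f the whole weeks elapsed since that subject started (0 to 7, mean 3.5). The mean of min(f, j) is 3.5 − 10.5/28 = 3.125, where 10.5 is the average of f(f + 1)/2.

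- Not yet dosed: 13.5 − 3.125 = 10.4.
- Others on drops: 3.125 enrolled after the index subject plus, by symmetry, 3.125 before, giving 6.25.

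Taking the first SAE when there may be more than one moves the event earlier. Simulation, conditional on at least one IVIG-arm SAE, gives about 11 not yet dosed at p = 2% and about 12 at 5%, with 6.2 others on drops. About half of those not yet dosed (5.3 to 5.7) would be in the IVIG arm.

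The single-SAE calculation at other enrolment speeds:

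| Enrolments per week | Not yet dosed | Others on drops |
|---|---|---|
| 0.5 | 13.5 − (1.5 − 2.5/28) = 12.1 | 2 × 1.41 = 2.8 |
| 1 | 10.4 | 6.25 |
| 2 | 13.5 − (7.5 − 42.5/28) = 7.5 | 2 × 5.98 = 12.0 |

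**The case against.** The strongest reply is that the study can already be halted. Section 8.6 contemplates a hold by the investigator, a regulator or another body, Section 8.1 requires IRB notice within 24 hours, and Section 8.8 sends reports to the FDA. That stands. A reader might infer that the plan leaves no power to stop after an SAE, and the documents do not support that. What is missing is a prespecified trigger.

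A reader might also infer that allergic and infectious SAEs are covered and only other kinds, such as a sterile corneal event, are left out. The counts above show otherwise.

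A third tempting reading is that the drops carry a known hazard. Section 1.9 reports no cytotoxicity and no excess staining at 4 mg/mL; the cytotoxicity it reports is at higher concentrations in cell culture. Section 1.10 found no rise in human IgG in mouse tissue or serum. Section 1.11.1 found smaller and fewer epithelial defects when IVIG was given with benzalkonium chloride than with benzalkonium chloride alone.

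On benefit, the count of subjects not yet dosed is a ceiling. It is reached only if nobody would otherwise have held the study and the review ends in no further dosing. If the IRB allows a restart, many of these subjects are dosed later.

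On cost, an automatic stop to dosing would be expensive. The tolerability endpoint runs from Day 1 to week 8, visit windows are ±4 days, and per-protocol means treatment completed as planned. Sections 5.6 and 5.7 also withdraw a subject whose study drug is withdrawn or discontinued. This objection stands, and it is why the fix pauses new exposure only.

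Finally, relatedness remains the investigator's judgement under Section 8.1. A trigger narrows that discretion but does not remove it.

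**Conclusion.** The point holds as a cheap improvement to consider. In the text available, no related SAE of any kind leads to a prespecified study-level pause; the plan relies on discretion, reporting and subject-level action. Confidence in that absence is high.

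The size is less certain, because every SAE and enrolment rate used is an assumption. At one enrolment per week at most about 11 to 12 subjects, roughly half of them in the IVIG arm, would be spared a first dose before review. The chance that the pause is used at all is about 25% to 35% at related-SAE rates of 1% to 2% on IVIG and 1% on saline.

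**What to change.** After the stopping sentence in Section 5.6, add:

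> After any SAE judged related to the study drops (either arm, masked; Section 8.1 causality guideline read as study drops), the IRB will be notified within 24 hours and no new subject will be enrolled or given a first dose until the IRB agrees. The IRB and investigator will decide whether subjects already on drops continue; an interruption for this review is not study-drug withdrawal under 5.6 or 5.7.

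The reference to study drops is needed because the guideline is worded for the active product ("There is a plausible temporal relationship between the onset of the AE and administration of the IVIG") while Section 5.7 keeps the assessors masked. Stating 24 hours makes clear that the Section 8.1 deadline applies here, not the 5 business days in Sections 8.6 and 8.8. The code-break option in Section 5.7 stays as it is.

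The cost is two sentences, with no new visit, test, staff or committee. When the trigger is met, enrolment is delayed for the length of the IRB review, sometimes for an event that proves unrelated or occurred on saline. Only if the IRB interrupts dosing might subjects already on drops lose per-protocol status: about 6 at one enrolment per week, about 3 at 0.5 and about 12 at 2.

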5.7 Rescue Plan

The research staff, including the PI, will be masked to randomization, thus will not be aware if a particular subject receives study drug or placebo. Subjects will be monitored by the Principal Investigator at each study visit. Any worsening of DED or any adverse event (AEs) will be recorded and in the case of AEs followed to resolution. In case of clinical worsening/ adverse event(s), based on the individual subject's clinical condition, one or more of the following therapeutic decisions may be implemented:

- (1) Increasing/adding the use of artificial tears or ointments,
- (2) Increasing/adding the use of anti-inflammatory therapy (Restasis/ Xiidra/ Steroids) or Serum Tears
- (3) Discontinue the study drug.
- (4) Other eye drops/measures (example, contact lens or surgeries), if indicated.

The decision will be made by the Principal Investigator based on his clinical judgment and the individual subject's clinical condition. If contact lens wear is reinstated and/or the study drug is discontinued, the subject will be withdrawn from the study. If an adverse event is severe enough to discontinue the subject from the study, the PI may decide to break the subject's randomization code if it seems relevant to the treatment of his/her ocular condition at that time. He/ She will receive the treatment required for his/ her eye condition as per established clinical guidelines.

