4.4.2 Data Collection and Follow-up for Withdrawn Subjects

If a subject withdraws from the study prior to 8 weeks, the subject will be asked to complete the procedures outlined in the 10 week visit as well as the Test Substance Tolerance scale from 8 weeks, as soon as possible. Subjects who voluntarily withdraw from the study between 8 weeks and 10 weeks will be asked to complete procedures outlined in the 10 weeks visit as soon as possible. Subjects who are withdrawn due to adverse events will be followed at least until resolution or stabilization of the adverse event.

If the subject remains in the study for safety evaluation, follow-up visits will be scheduled according to the schedule of visits and procedures found in the synopsis.

5 Study Drug

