6.5.4 Visit 4: Week 8 (\pm 4 days)

Treatment Visit (after any dose for that day)

- Review the subject's diary and record changes in concomitant medication, deviations from drug schedule and adverse events.
- Vital Signs: Blood pressure, Pulse, and Temperature taken while subject is in a sitting position.
- Visual Acuity (Snellen's chart) with eye glasses (if applicable)
- OSDI
- Symptom Intensity Assessment, SGA and CGA
- Test Substance Tolerance (VAS)
- Keratograph Oculus Redness Score
- > Non-invasive Keratography Tear Film Break-up Time (NIK BUT)
- Schirmer I test
- Baseline Ophthalmic Examination (slit lamp examination, VBR)
- Ocular surface wash collection for analysis (Potential biomarkers)
- InflammDry Test for MMP-9 Protein
- Lissamine Dye Corneal and Conjunctival staining
- Intraocular pressure measurement after topical anesthesia to eye
- **Returning of unused study drug/ placebo (by patient to pharmacy)**

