6.5.5 Visit 5: Week 10 (\pm 4 days)

Follow-Up Visit

- Review the subject's diary and record changes in concomitant medication and adverse events.
- Vital Signs: Blood pressure, Pulse, and Temperature taken while subject is in a sitting position.
- Visual Acuity (Snellen's chart) with eye glasses (if applicable)
- OSDI
- Symptom Intensity Assessment, SGA and CGA
- Baseline Ophthalmic Examination (slit lamp examination, VBR)

- **Returning of patient diary (by patient to PI)**

7 Statistical Plan

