7.2 Statistical Methods

Based on the classification of reasons for conducting pilot studies by Thabane et al, in this pilot study we will assess the following: (i) Process– recruitment rate, retention rate, (non)compliance or adherence rate; and (ii) Scientific– safety (adverse event/SAE rate), tolerability, and efficacy, including reduction in clinical signs and symptoms (OSDI, Corneal staining, Redness etc as detailed in section 3.4) and treatment effect size. We will calculate the observed rate with 95% confidence interval for each rate by treatment group. Other descriptive statistics, including median with interquartile or mean with standard deviation for continuous variables and frequency with percentage for categorical variables will be reported as well. To estimate the preliminary efficacy under the scientific category, one eye (target eye) will be selected at screening visit as follows: (i) if only 1 eye meets inclusion criteria, this eye is used; (ii) if both eyes meet inclusion criteria, the eye with the higher corneal stain score is used; (iii) if both eyes have the same corneal stain score, then the one with the lower Schirmer I score is used; (iv) if both eyes have same scores, the right eye is used. Secondary analyses will be performed for the non-target eye as well. Due to the nature of this feasibility study, any efficacy statistical tests and adjusted analyses will not be conducted. Detailed data validation will examine completeness, existence and accuracy of collected data to assess data quality and identify missing and conflicting data. Statistical analysis will be performed on an intention-to-treat basis i.e., inclusion of all patients randomly assigned, regardless of adherence, actual treatment received, and subsequent withdrawal of treatment and/or deviation from the protocol and per-protocol (i.e., inclusion of those who completed the treatment as planned) and will be reported according to 2010 CONSORT guidelines. All statistical analyses will be completed using SPSS Statistics V.22.0.31

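### A subject withdrawn before Week 8 has no required post-baseline value on seven exploratory endpoints, so their ITT summaries become observed-case summaries

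*Combined protocol and SAP*

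**What the plan says.** **Routes to withdrawal.** Section 5.7: "If contact lens wear is reinstated and/or the study drug is discontinued, the subject will be withdrawn from the study". Section 5.6 agrees: if "contact lens wear is instituted during the course of the study and/or the study drug is withdrawn, the subject will be withdrawn". Section 5.6 also withdraws subjects with a presumed ocular allergic reaction or an ocular infection. Section 4.4.1 adds voluntary withdrawal and withdrawal by the investigator or IRB. Other rescue options, such as "Increasing/adding the use of anti-inflammatory therapy (Restasis/ Xiidra/ Steroids) or Serum Tears", do not by themselves trigger withdrawal under section 5.7.

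**The withdrawal visit.** Under section 4.4.2, a subject who leaves before Week 8 will be "asked to complete the procedures outlined in the 10 week visit as well as the Test Substance Tolerance scale from 8 weeks". The section then adds: "If the subject remains in the study for safety evaluation, follow-up visits will be scheduled according to the schedule of visits and procedures".

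**What is measured when.** The Week 8 list (6.5.4) includes "Lissamine Dye Corneal and Conjunctival staining", Schirmer I, NIK BUT, Keratograph redness, InflammaDry and the ocular surface wash. The Week 4 list (6.5.3) and Week 10 list (6.5.5) contain none of these. The schedule of visits agrees, and section 3.6 confirms it for the wash.

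**The analysis.** Section 7.2 defines ITT as "inclusion of all patients randomly assigned, regardless of adherence, actual treatment received, and subsequent withdrawal of treatment and/or deviation from the protocol". On missing data it says only that they will be identified.

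**The concern.** The ITT definition covers subjects who stop treatment, but the visit meant to capture their data leaves out six procedures that have no other post-baseline visit before or after Week 8. With no rule for missing values, the ITT summary of any endpoint based on those procedures can use only the subjects who reached Week 8, which moves it toward the per-protocol set.

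The loss is unlikely to be random. Under sections 5.6 and 5.7 the forced withdrawals follow clinical worsening or an adverse event, so the missing values may tend to be poor ones. Section 5.6 itself accepts that stopping lens wear may raise the risk of worsening.

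Two uses of the data are at stake. Section 1.5 says the results will guide the choice of primary or co-primary endpoint for later studies, and section 7.1 wants SDs for the next sample size calculation.

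**Working it through.** **1. Which endpoints are affected.** The 15 endpoints of section 3.4, set against the Week 10 list that section 4.4.2 calls for:

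| Collected at the withdrawal visit | Not collected (Week 8 only after baseline) |
|---|---|
| 1 OSDI | 2 Schirmer I |
| 5 VBR redness | 3 corneal staining clearance |
| 6 visual acuity | 4 corneal staining score |
| 7 artificial tear or drop frequency | 12 NIK BUT |
| 8 filaments, 9 mucoid films | 13 Keratograph redness |
| 10 CGI, 11 SGA | 14 MMP-9 |
| | 15 cytokines in wash |
| **8 of 15** | **7 of 15** |

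The tolerance VAS (the primary endpoint), symptom intensity, vital signs and adverse events are also collected at the withdrawal visit.

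**2. The plan's own attrition figure.** Section 7.1 has 12 per arm and 10% attrition: 12 / 0.9 = 13.3, rounded up to 14 per arm, and 14 x 2 = 28, as stated. The literal expectation is 0.10 x 28 = 2.8, about 3 subjects. The full allowance is 28 - 24 = 4. Both are all-cause; the documents give no rate for withdrawal before Week 8 or for rescue.

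**3. Effect on an arm's mean (illustration).** Assume 14 per arm (section 3.1), a normal outcome, and that the k subjects with the worst trigger score are lost. Rho is the assumed correlation between trigger and outcome. Improvement in the mean of those left, in SD, from 200,000 simulated samples:

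| k lost of 14 | rho 0.5 | rho 1 |
|---|---|---|
| 1 | 0.067 | 0.131 |
| 2 | 0.121 | 0.243 |
| 3 | 0.173 | 0.347 |
| 4 | 0.225 | 0.447 |

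At rho 0 the shift is about zero.

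**4. Effect on the difference between arms** (one arm's shift minus the other's, at rho 0.5 and rho 1):
- 3 losses split 2/1: 0.121 - 0.067 = 0.05; 0.243 - 0.131 = 0.11.
- 4 losses split 2/2: 0.
- 4 losses split 3/1: 0.173 - 0.067 = 0.11; 0.347 - 0.131 = 0.22.
- 4 losses split 4/0: 0.22; 0.45.

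The sign depends on which arm loses more subjects.

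**5. Yardstick.** The 95% CI half-width for a difference in means is t(0.975, 22) x sqrt(1/12 + 1/12) = 0.85 SD at 12/12, and t(0.975, 22) x sqrt(1/10 + 1/14) = 0.86 SD at 10/14.

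**6. Precision of the SD.** Losing 3 of 28 moves the 95% CI factors for a pooled SD from 0.79-1.37 (n = 28, 26 df) to 0.78-1.40 (n = 25, 23 df). The fewer subjects cost little precision; the issue is which subjects are missing.

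**The case against.** The strongest reply is that this is a pilot with no primary efficacy endpoint and no efficacy tests, that the seven endpoints are descriptive, and that few subjects are involved. All of that stands, and it is why the point is minor. It does not explain leaving the measurements out.

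Section 5.6 gives a sound reason for restricting lenses: they reduce staining directly. That supports the restriction, but it does not argue against measuring before a lens is fitted, and it does not apply to someone who only stops the drug.

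Section 4.4.2 keeps the visit schedule for a subject who stays in for safety evaluation, which may recover some values. But sections 5.6 and 5.7 say these subjects leave the study, and the weekly follow-up after worsening in section 5.6 names none of the six procedures.

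A reader might infer four stronger things that the documents do not support:

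- *That ITT cannot include these subjects.* They remain in the ITT set, with tolerance, safety and eight exploratory endpoints. The gap is confined to seven endpoints and to withdrawal before Week 8.
- *That the rescue rule is the defect.* The gap comes from the visit content in section 4.4.2 and applies to every early withdrawal, voluntary ones included.
- *That staining and Schirmer will look better than OSDI and VBR when the later primary endpoint is chosen.* Section 7.2 has no rule placing any withdrawal-visit value in a Week 8 summary, so OSDI, VBR and the tolerance VAS could lose the same subjects.
- *That the bias favors IVIG.* If more placebo subjects are withdrawn, the apparent IVIG effect shrinks. The investigator who chooses rescue is masked.

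**Conclusion.** The gap is real and can be read directly from the text: for a subject withdrawn before Week 8, seven of 15 exploratory endpoints have no required post-baseline value, and section 7.2 does not say how an ITT summary should treat that. Those summaries become observed-case summaries that may lack subjects who worsened.

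The severity is minor. At about 3 losses split 2/1, the illustrated shift between arms is 0.05 to 0.11 SD. Reaching 0.45 SD needs all four losses in one arm and a perfect correlation between trigger and outcome. Both are below the CI half-width of about 0.85 SD, and the direction is unknown. The illustration assumes that the whole section 7.1 allowance falls before Week 8 and is driven by worsening, which the documents do not state. The endpoint count needs no such assumption.

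**What to change.** **Section 4.4.2.** For withdrawal before Week 8, replace the Week 10 procedures plus tolerance scale with the Week 8 visit procedures (6.5.4) and return of the diary. State that, where clinically safe, the visit takes place before a lens is fitted or other rescue starts. The Week 8 list already holds every Week 10 assessment and the tolerance scale, so nothing is lost.

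**Section 7.2.** Add one rule for all endpoints, including OSDI, VBR and the tolerance VAS: show the observed Week 8 values, and beside them a summary that uses the withdrawal-visit value where Week 8 is missing, with the number of each by arm. A rule for the seven endpoints alone would treat endpoints unevenly.

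**Cost.** About 3 to 4 longer visits if losses match section 7.1, using tests the site already runs, and a few sentences of text. The sample size does not change. For subjects who attend, the gap falls from 7 of 15 endpoints to 0 of 15.

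**Downsides.** Some withdrawn subjects will not attend. A withdrawal-visit value is earlier than Week 8 and may be taken at the subject's worst, so it can overstate lasting worsening. Staining in a subject already back in lenses is affected by the lens. Showing the two summaries side by side lets the reader see how much this matters.
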